
PLANNED TRIAL PERIODS
	
The total duration of the study will be approximately 33 months, including approximately 24 months of active enrolment.
 
Consenting patients will be followed until death, or until the date of study termination, whichever occurs first.
 
 • Planned start date (first patient on study): 3Q09. • Planned enrolment period: 24 months. • Planned study termination (clinical cutoff): six months after the last treatment visit of the last evaluable patient included in the study or nine months after the last patient is included, whichever occurs first.

SCHEDULE OF ASSESSMENTS AND PROCEDURES

	Screening	Treatment (cycle 1 and further cycles)					Follow-up (1)
Study day	D-28 to D1	D1	D8 D15	D22	D28 (=D1 of the next cycle)	End of treatment (last dose + 30 days)	
Study visit window			Within 2 days of pre-specified day				
Written informed consent	Before any study procedure						
Medical history	•						
Complete physical examination	•	•	Repeat if clinically indicated			•	• (9)
ECOG PS	•	•	Repeat if clinically indicated			•	• (9)
Vital signs	•	•	•		•	•	• (9)
Weight and height	•	Repeat if clinically indicated			•	Repeat if clinically indicated	
Hematology	• (2)	• (2)	• (7)	• (7)	• (7)	•	•
Biochemistry A	• (2)	• (2)	• (7)	• (7)	• (7)	•	•
Biochemistry B	• (2)	Repeat if clinically indicated			• (7)	•	•
Calculated creatinine clearance	• (2)	Repeat if clinically indicated			•	Repeat if clinically indicated	
Pregnancy test	• (3)	Repeat if clinically indicated					
ECG	• (10)	Repeat if clinically indicated			•	•	•
LVEF (cardiac ultrasound)	• (10)	Repeat if clinically indicated			• (8)	•	•
Intercurrent events, concomitant disease and treatments	•	Throughout the “on treatment” period					• (1,9)
Adverse events	NA	Throughout the “on treatment” period					• (1)
Tumor assessment	• (4)	Every other cycle (± 1 week) until PD				•	• (9)
Other tests	•	When indicated, according to the clinical and laboratory context					• (9)
Pharmacokinetics		• (5)	• (5)				
PGx substudy, if patient consented		• (6)					

1. Patients withdrawn with PM00104-related ongoing AEs should be followed with the appropriate tests until their resolution. Beyond 30 days after the last administration of study drug, only those procedures that are relevant to any remaining toxicities need to be performed.

-

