2. Within one week prior to the first administration of PM00104. Repeat on Day 1 of Cycle 1 prior to treatment with PM00104, if the treatment is administered more than one week after the screening test.

Hematology: differential WBC (neutrophils, lymphocytes), hemoglobin and platelets.

Biochemistry A: liver function test (ALT, AP, AST, LDH, total and direct bilirubin), creatinine, CPK, troponin I, glucose and serum electrolytes (Na⁺, Cl⁻, K⁺, Ca⁺⁺, Mg⁺⁺).

Biochemistry B: total protein, albumin, amylase and lipase. CPK-MB fraction to be analyzed if CPK and/or troponin I are abnormal. In the case of grade ≥ 3 increase in serum cardiac troponin I, an ECG and cardiac ultrasound will be performed as soon as possible.

3. Pregnancy test, if applicable, within two weeks prior to registration
4. CT-scan or MRI of all measurable/evaluable sites of disease, as per RECIST. Within four weeks prior to the first dose of PM00104. Documentation of PD is mandatory.
5. First two infusions of the first cycle only.
6. Tissue block collection. Additionally, one blood sample will be taken prior to the first infusion of PM00104.
7. To be performed within the two prior days. If NCI-CTCAE grade ≥ 3 occurs, the appropriate chemistry test(s) should be done at least every 2-3 days until recovery.
8. To be performed every other cycle.
9. After discontinuation, patients taken off study without PD should be monitored every three months until PD, death, other antitumor therapy or the predefined date for study termination. After PD, patients should be monitored every three months until death or the predefined date for study termination.
10. All ECGs and LVEFs (ultrasound) will be reviewed by an external cardiologist.

AE, adverse event; ALT, alanine aminotransferase; AP, alkaline phosphatase; AST, aspartate aminotransferase; CPK, creatine phosphokinase; CPK-MB, creatine phosphokinase-fraction MB; CT, computed tomography; ECG, electrocardiogram; ECOG, Eastern Cooperative Oncology Group Performance Status; LDH, lactate dehydrogenase; LVEF, left ventricular ejection fraction; MRI, magnetic resonance imaging; NA, not applicable; NCI-CTCAE, National Cancer Institute Common Terminology Criteria for Adverse Events; PD, progressive disease; RECIST, Response Evaluation Criteria In Solid Tumors; WBC, white blood cells.

LIST OF ABBREVIATIONS AND DEFINITION OF TERMS

ΔT/ΔC	% Ratio of Treated versus Control Tumor Volumes
AE(s)	Adverse Event(s)
ALT	Alanine Aminotransferase

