5.7. EVALUATIONS DURING TREATMENT

The following assessments will be done while the patient is on treatment ([Table 9](#)). A 2-day window is allowed for the different tests and procedures.

Table 9. Evaluations during treatment.

	ASSESSMENT	TIME
1. Clinical examination	
 ♦ Complete physical examination. ♦ Performance status (ECOG PS; see Appendix 2. ECOG Performance Status Assessment Scale). 	Day 1 of the first cycle prior to the PM00104 infusion, and then whenever clinically indicated.
	
 ♦ Vital signs: heart rate, blood pressure and body temperature. 	Before any PM00104 infusion.
	
 ♦ Weight and height. 	Repeat on Day 1 of each cycle prior to the PM00104 infusion, and then whenever clinically indicated.
	
 ♦ Intercurrent events, concomitant disease and treatments. 	Throughout the “on treatment” period (i.e., treatment plus 30 days following the last PM00104 administration).
2. Laboratory tests	
 ♦ Hematology: differential WBC (neutrophils, lymphocytes), hemoglobin and platelets. ♦ Biochemistry A: liver function tests (AP, ALT, AST, LDH, total and direct bilirubin), creatinine, CPK, troponin I, glucose and serum electrolytes (Na⁺, Cl⁻, K⁺, Ca⁺⁺, Mg⁺⁺). 	Repeat on Day 1 of each cycle prior to the PM00104 infusion, and then weekly. If NCI-CTCAE grade ≥ 3 occurs, the appropriate test(s) should be repeated at least every 2-3 days until recovery.
	
 ♦ Biochemistry B: total protein, albumin, amylase and lipase. CPK-MB fraction to be analyzed if CPK and/or troponin I are abnormal. In the case of grade ≥ 3 increase in serum cardiac troponin I, an ECG and cardiac ultrasound will be performed as soon as possible. 	Repeat on Day 1 of each cycle prior to the PM00104 infusion, and then whenever clinically indicated. If NCI-CTCAE grade ≥ 3 occurs, the appropriate test(s) should be repeated at least every 2-3 days until recovery.
3. Calculated creatinine clearance	Calculated using the Cockcroft and Gault formula (see Appendix 3. Cockcroft and Gault Formula).	Repeat on Day 1 of each cycle prior to the PM00104 infusion, and then whenever clinically indicated.

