7.2.3.1. Hematological Toxicity

The PM00104 dose administered to the patients will be reduced based on the nadir value of the platelet count and the ANC measured in the preceding cycle. In the event of a platelet count < 25 x 10⁹/l or an ANC < 0.5 x 10⁹/l lasting ≥ 5 days or associated with fever, sepsis or infection in the preceding cycle, the dose administered to the patient in following cycles will have to be reduced by one level ([Table 13](#)). In addition, re-treatment on the next infusion will only be allowed if the patient fulfils all pertinent criteria (see Section [7.2.2](#)).

Table 13. Dose adjustments due to hematological toxicity.

Toxicity	PM00104 dose
Grade 4 neutropenia (ANC < 0.5 x 10 ⁹ /l) lasting ≥ 5 days. Grade 4 neutropenia with fever (≥38.5°C). Grade 4 neutropenia with sepsis or severe infection.	Decrease one dose level
Thrombocytopenia. Platelets < 25 x 10 ⁹ /l	Decrease one dose level

Any dose reductions due to treatment-related hematological toxicities other than those listed in [Table 13](#) will have to be discussed and agreed with the Sponsor.

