A Simon two-stage design will be adopted in this group to test the null hypothesis that the ORR by RECIST is $\leq 5\%$ *versus* the alternative that $\text{ORR} \geq 20\%$ (two-sided test; $\alpha=0.1$ and $\beta=0.1$). A maximum of 32 evaluable patients will be included in this group. In a first stage, 18 evaluable patients will be recruited. If one or more (≥ 1) patients achieve an objective response, the accrual in this group will be expanded with 14 additional evaluable patients. If the total number of patients with objective response is 4 or more (≥ 4) in 32 evaluable patients (i.e., an ORR in the whole study of at least 12.5%), the null hypothesis will be rejected and PM00104 will be considered for further clinical development in cervical cancer.

Early stopping rule

An early stopping rule for excessive toxicity will be evaluated when ten patients in each group will be recruited and followed for at least four weeks. A "serious toxicity" rate (STR) of 40% or more will be considered inadequate. The following are considered serious toxicities:

- Drug-related grade 4 neutropenia lasting for more than seven days.
- Grade 4 thrombocytopenia.
- Grade 3/4 nausea/vomiting despite adequate prophylaxis.
- Grade 3/4 transaminase increase lasting for more than seven days.
- Grade 3/4 fatigue.
- Any other grade 3/4 drug-related event leading to early study discontinuation.

If ≥ 4 patients of the first 10 patients had one of these serious toxicities, the trial will be stopped and the recommended dose and/or administration schedule for phase II will be re-evaluated.

With this stopping rule, the probability of $\geq 4/10$ STR in the sample (if the true probability of STR is $< 1/6$) is 0.0697. On the other hand, the probability of observing $\leq 3/10$ STR in the sample (if the true probability of STR is $> 40\%$) would be 0.3822.

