N° of days with grade 3-4 neutropenia			
Day of recovery to grade ≤ 1			
Platelets			
Day of nadir platelets count			
Nadir of platelets count (/mm ³)			
Day of thrombopenia G3-4 onset			
Day of recovery to grade ≤2			
N° of days with grade 3-4 thrombopenia			
Day of recovery to grade ≤ 1			

Programming notes: (*)Denominator = N of patients with Grade 3-4

Table 12.3.1. 6 Baseline grade and evolution of hematological toxicities.

	Worst grade per patient							
	Grade 0-		Grade 2		Grade 3		Grade 4	
	N	%	N	%	N	%	N	%
Anemia (Baseline)								
Grade 0-1								
Grade 2								
Grade 3								
Grade 4								
Neutropenia (Baseline)								
Grade 0-1								
Grade 2								
Grade 3								
Grade 4								
.....								
Grade 0-1								
Grade 2								
Grade 3								
Grade 4								

12.3.2 Biochemistry abnormalities.

Table 12.3.2. 1 Biochemistry worst grade per patient.

	Grade 1		Grade 2		Grade 3		Grade 4		Total	
	N	%	N	%	N	%	N	%	N	%
AST										
ALT										
Total Bilirubin										
Direct Bilirubin										
....										

Programming Notes: Percentages are based on the safety population.

Table 12.3.2. 2 Biochemistry worst grade per cycle.

	Grade 1		Grade 2		Grade 3		Grade 4		Total	
	N	%	N	%	N	%	N	%	N	%
AST										
ALT										
Total Bilirubin										
Direct Bilirubin										
....										

Programming Notes: Percentages are based on the safety population.

Table 12.3.2. 3 Supportive listing: Patients with any Biochemistry abnormalities grades 3-4.

Patient ID	Lab. test	Cycle	Examination date	N	Std. val	xLLN	Grade

Listing 12.3.2. 4 Listing of patients with biochemistry evaluations missing.

Patient	Cycle	Lab. tes

Table 12.3.2. 5 Time course and recovery from biochemistry toxicities.

	N	All cycles Median	Range
ALT			
Day of peak ALT count			
Nadir of ALT count (/mm3)			
Day of ALT G3-4 onset			
Day of recovery to grade ≤2			
N° of days with grade 3-4 ALT increase			
Day of recovery to grade ≤ 1			
AST			
Day of peak AST count			
Nadir of AST count (/mm3)			
Day of AST G3-4 onset			
Day of recovery to grade ≤2			
N° of days with grade 3-4 AST increase			
Day of recovery to grade ≤ 1			

Programming notes: (*) Denominator= N of patients with Grade 3-4.

Table 12.3.2. 6 Baseline grade and evolution of Biochemical toxicities.

	Worst grade per patient							
	Grade 0-1		Grade 2		Grade 3		Grade 4	
	N	%	N	%	N	%	N	%
ALT (Baseline)								
Grade 0-1								
Grade 2								
Grade 3								
Grade 4								
AST (Baseline)								
Grade 0-1								

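### Schedule note 7 limits the 2-3-day repeat tests to chemistry while Table 9 includes blood counts; a site following note 7 literally cannot reliably tell whether grade 4 neutropenia lasted ≥5 or >7 days

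*Protocol*

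**What the plan says.** **Repeat testing, first place.** In the protocol's Schedule of Assessments and Procedures the Hematology row begins "Hematology • (2) • (2) • (7) • (7) • (7"; the bracketed figures are note numbers. Note 7 therefore governs the counts at D8/D15, D22 and D28. After a sentence on timing, it reads "If NCI-CTCAE grade ≥ 3 occurs, the appropriate chemistry test(s) should be done at least every 2-3 days until recovery". Blood counts are not named.

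**Repeat testing, second place.** Table 9 in protocol section 5.7 has one laboratory cell that holds both "Hematology: differential WBC (neutrophils, lymphocytes), hemoglobin and platelets" and Biochemistry A. Its timing column asks for tests on Day 1 of each cycle and weekly after that. After a grade 3 or higher event, "the appropriate test(s) should be repeated at least every 2-3 days until recovery". That wording includes blood counts.

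**Where duration is used.**
- Stopping rule (protocol 10.1, repeated in SAP 6.2): one of the serious toxicities is "Drug-related grade 4 neutropenia lasting for more than seven days". Four or more affected patients among the first 10 stop the trial.
- Dose rule (protocol 7.2.3.1): grade 4 neutropenia leads to a reduction if "lasting ≥ 5 days or associated with fever, sepsis or infection in the preceding cycle".
- SAP Table 12.3.1.5 reports "N° of days with grade 3-4 neutropenia".

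Neither document says which repeat-testing text governs, or how a duration is obtained from counts taken some days apart.

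**The concern.** Note 7 is attached to the blood-count row and then leaves blood counts out of its repeat-test sentence. A site working from the schedule page could follow it to the letter and keep counts weekly through an episode of grade 4 neutropenia. A site working from Table 9 would repeat counts every 2-3 days.

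The two limits that matter are five days and seven days, which are no longer than the weekly interval itself. Whether a patient counts towards the stop, or meets the duration trigger for a dose reduction, could then depend on which page the site used and on when the visits fell.

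**Working it through.** **1. The plan's own figures.** The stopping-rule probabilities reproduce as exact binomials with n = 10:
- P(X ≥ 4 | 1/6) = 0.0697 (stated 0.0697).
- P(X ≤ 3 | 0.40) = 0.38228 (stated 0.3822, truncated).

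Both take each patient's toxicity status as known. The documents give no figure for how precisely durations are measured.

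**2. What weekly counts can bound.** With k consecutive grade 4 counts 7 days apart, and a count that is not grade 4 on either side, the true length lies between 7(k − 1) and 7(k + 1) days.
- k = 1: 0 to 14 days. Neither ≥5 nor >7 is confirmed or excluded.
- k = 2: 7 to 21 days. The ≥5-day limit is met; more than seven is not proven at exactly 7-day spacing.

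In cycle 1 the scheduled post-dose counts are D8, D15, D22 and D28. The gaps are 7, 7 and 6 days, so no adjacent pair is nominally more than seven days apart.

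**3. How often two grade 4 counts are seen.** Assume exact weekly spacing and an onset uniformly placed between two counts. For a true length d between 7 and 14 days, P(two grade 4 counts) = (d − 7)/7.

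| True length (days) | Two grade 4 counts |
|---|---|
| 5 to 7 | 0 (at exactly 7 days only in the limit) |
| 8 | 1/7 = 14% |
| 10 | 3/7 = 43% |
| 12 | 5/7 = 71% |
| 14 | 7/7 = 100% |

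A 5-day episode falls wholly between counts with probability (7 − 5)/7 = 29%.

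**4. The visit window.** The schedule allows visits "Within 2 days of pre-specified day". Two adjacent counts may therefore be 7 − 4 = 3 to 7 + 4 = 11 days apart. Two grade 4 counts 3 days apart do not show five days; two that are 11 days apart show more than seven.

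**5. The same check with 2-3-day repeats of blood counts.** Let repeats every g = 2 or 3 days start at the first grade 4 count.
- One grade 4 count followed by recovery bounds the length at 0 to 7 + g, so 9 or 10 days instead of 14. If a grade 3 count had already started the repeats, the bound is 2g, so 4 to 6 days.
- The observed grade 4 span reaches 5 days with probability (d − 6)/7 for either g: 29%, 57% and 86% at 8, 10 and 12 days.

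This narrows the uncertainty without removing it: onset can still lie up to 7 days before the first low count.

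**6. Effect on the stop, as illustration only.** Let p = 0.40 be the true serious-toxicity rate, f the share of those toxicities that qualify only through neutropenia duration, and m the share of those that go uncounted. The counted rate is q = p(1 − fm).
- f = 0: q = 0.40, P(stop) = 0.618.
- f = 0.25, m = 0.25: q = 0.375, P(stop) = 0.553.
- f = 0.5, m = 1: q = 0.20, P(stop) = 0.121.

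Neither f nor m is in the documents, so this shows the mechanism and is not an estimate.

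**The case against.** **Table 9 is equally part of the protocol.** A site that follows it also satisfies note 7, which sets only a minimum and forbids nothing. Because note 7 hangs on the Hematology row, its restriction to chemistry may be a slip. This stands: the problem exists only where note 7 is read literally. The documents do not say that any site will do so, and they do not rule it out.

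**Random phase is unsupported.** Infusions and counts share one calendar, so nadirs will not fall evenly between counts. This stands, and the percentages in step 3 are conditional on that assumption. The 0-to-14-day bound for a single count needs only the nominal spacing.

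**There are backstops.** Low neutrophils on both Day 8 and Day 15 cause both infusions to be skipped, which should end treatment unless there is clear benefit. The stopping rule also counts other drug-related grade 3/4 events that lead to early discontinuation. This stands in part: it reaches only lows on those two days, and section 5.2.1 defines treatment and study discontinuation separately, so whether such a case counts is not certain. The fever, sepsis, infection and platelet triggers need no duration, and the transaminase item is chemistry; none of these is affected.

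**Few events may turn on it.** Section 1.3.5.5.2 describes neutropenia as short-lasting, with a low grade 3/4 rate at the chosen dose and no infusions skipped because of it. This stands and points to the milder end of step 6.

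**Conclusion.** The two passages conflict in operative text, and they should be reconciled. Where note 7 is followed literally, weekly counts cannot reliably show whether grade 4 neutropenia lasted at least five days or more than seven. Episodes near those limits mostly yield one grade 4 count, and within the visit window the classification depends on visit timing. The size rests on nominal spacing and random phase; the effect on the 4-in-10 count is not known from the documents.

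A reader might infer more: that these durations cannot be measured at all, or that more than seven days can never be shown for an episode of up to 14 days. The documents do not support that. Table 9 calls for 2-3-day counts, two weekly grade 4 counts at nominal spacing establish five days, and the visit window lets two adjacent counts span more than seven.

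**What to change.** 1. **Protocol:** reconcile note 7 of the Schedule of Assessments with Table 9, so that a single repeat-test requirement is stated for blood counts and for chemistry.
2. **SAP:** have the sponsor state one derivation of duration from spaced counts, including how onset between visits is handled. It must use the grade that each output uses: grade 4 in the stopping rule, grade 3-4 in Table 12.3.1.5. Measuring from first to last grade 4 value everywhere would not do. It would misdefine that table, and it shortens durations systematically, because time before the first and after the last low count is dropped.

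No view is taken here on which monitoring, dose or stopping rule is right.

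**Cost:** a wording change to one schedule note and a short addition to the SAP. If the sponsor aligns the passages to Table 9, extra blood counts arise only at sites that had followed note 7 literally.

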1. INTRODUCTION

1.1. ENDOMETRIAL CANCER

Uterine corpus cancer includes endometrial carcinoma (90%) and mixed histology (10%) (1). The 75-80% of endometrial carcinomas are endometrioid adenocarcinomas, with variants such as adenosquamous, villoglandular, ciliated and secretory subtypes. Rare cell types, including uterine papillary serous carcinoma (UPSC), clear cell carcinoma, papillary endometrioid carcinoma, and mucinous carcinoma have a later age of onset, greater risk for extrauterine metastases, and poorer prognosis compared with typical low grade adenocarcinomas.

[Table 1](#) outlines the incidence and mortality figures for uterine corpus cancer in the USA and Europe (no statistics are available for endometrial cancer alone). In 2008, it was estimated that 40,100 new cases of uterine corpus cancer will be found in the USA and 7,470 deaths will occur due to this disease (2). Thus, uterine corpus is the first genital cancer in females with respect to estimated new cases in the USA (6% of all cancer cases), and the second cause of gynecologic cancer mortality (3% of deaths due to cancer), immediately after ovarian cancer.

Table 1. Incidence and mortality due to cancer of the uterus (corpus and cervix)§.

	Incidence*	Mortality**
Uterine corpus cancer		
USA†	40,100	7,470
European Union ††	82,230	25,740
Uterine cervix cancer		
USA†	11,070	3,870
European Union ††	30,560	13,650

*Number of new cases per year.

**Number of deaths per year.

[figure not shown]
†Source: Jemal *et al.* Cancer statistics, 2008. *CA Cancer J Clin.* 58:71-96 (2008) (2).

††Source: Arbyn *et al.* Burden of cervical cancer in Europe: estimates for 2004 *Ann Oncol* 18:1708-1715 (2007) (3).

§In both statistical analyses/databases, no data for endometrial cancer alone are provided. They are included with other types of cancer characteristic of uterine corpus cancer (uterine sarcoma, etc.).

Cancer of the uterus is among the cancers for which survival has not improved substantially over the past 25 years ([Figure 1](#)), making its treatment an important public health issue. The 5-year survival rates are drastically reduced in those patients with regional disease at diagnosis (56%) or with distant disease (17%) (2). Therefore, patients with metastatic disease have a dismal survival.

Figure 1. Annual age-adjusted* cancer death rates among females for selected cancers (USA, from 1930 to 2004).

*Rates are age-adjusted to the 2000 USA standard population. †“Uterus” includes uterine corpus and uterine cervix. Figure drawn from Jemal *et al.* Cancer Statistics 2008. *CA Cancer J Clin.* 58:71-96 (2008) (2)

Most patients with endometrial cancer have stage I disease at diagnosis and, therefore, surgery (usually total abdominal hysterectomy, with bilateral salpingo-oophorectomy) is the treatment of choice (1). Primary radiotherapy is administered for medically inoperable patients and adjuvant radiotherapy is offered for those patients at high risk of recurrence.

For metastatic extra-abdominal disease, palliative therapy including radiotherapy, hormonal therapy, or chemotherapy is generally used with poor results (4).

1.1.1. Treatment of Advanced/Metastatic Endometrial Cancer

Surgery (with or without radiotherapy) is recommended for patients with recurrence at sites without prior radiotherapy or with previous brachytherapy only. Recommended salvage therapy for patients with recurrence at sites previously irradiated includes pelvic exenteration with or without intraoperative radiotherapy, hormonal therapy or chemotherapy (4). Treatment with systemic agents should be considered for those patients with advanced or recurrent disease not amenable to radiation or surgery.

Hormonal therapy for metastatic disease involves mainly the use of progestational agents, although aromatase inhibitors are also being used (4).

Although phase II/III data is limited, chemotherapy for endometrial cancer includes different single agents, such as cisplatin, carboplatin, oxaliplatin, paclitaxel, docetaxel and doxorubicin (5, 6). Response rates in first-line chemotherapy with these compounds range 20-30% for single-agent regimens and 40-60% for combinations. However, despite these relatively high response rates, most patients progress after a median of 6-9 months and are candidates for second-line therapy. Results of second-

line chemotherapy are generally poor, and only taxanes (e.g., paclitaxel) have shown response rates greater than 20% in this disease setting ([Table 2](#)).

Table 2. Antitumor activity of different single-agent therapies administered as second-line chemotherapy in recurrent, advanced endometrial carcinoma.

Agent	Reference	No of patients	Schedule (dose)	Median ORR (%)
Cisplatin	Thigpen et al. (7)	25	q3wk (50 mg/m ²)	4.0
Docetaxel	García et al. (8)	27	1-hour Day 1, 8 and 15 q4wk (36 mg/m ²)	7.7
Flavopiridol	Grendys et al. (9)	26	i.v. bolus Day 1, 2 and 3 q3wk (50 mg/m ² /day)	0.0
Ifosfamide	Sutton et al. (10)	52	Daily for 5 days q4wk (1.2 g/m ²)	15.0
Irofulven	Schilder et al. (11)	25	Daily for 4 days (11 mg/m ²)	4.0
Ixabepilone	Dizon et al. (12)	NA	NA	12.0
Liposomal doxorubicin	Muggia et al. (13)	46	1-hour q4wk (50 mg/m ²)	9.5
Oxaliplatin	Fracasso et al. (14)	44	2-hour q3wk (130 mg/m ²)	13.5
Paclitaxel	Lincoln et al. (15)	44	3-hour q3wk (200 mg/m ²)	27.3
	Homesley et al. (16)	16	1-hour weekly (80 mg/m ²)	26.7
Pyrazoloacridine	Plaxe et al. (17)	23*	3-hour q3wk (750 mg/m ²)	4.3
Topotecan	Miller et al. (18)	29	Daily for 5 days q3wk (0.5-1.5 mg/m ²)	9.0

*11 of 23 patients pretreated.

NA, non available; ORR; overall response rate; q3wk; every three weeks; q4wk, every four weeks.

Two combination regimens of chemotherapy have been tested in phase III clinical trials in the first line: doxorubicin/cisplatin/paclitaxel (19)) and cisplatin/doxorubicin (19-23)(19-23). The first regimen was the most active, but also the most toxic, in particular with respect to neurotoxicity (24). Overall response rate (ORR) ranged from 42% (cisplatin/doxorubicin) to 57% (doxorubicin/cisplatin/paclitaxel), but the duration of response was relatively short, and the median survival was approximately one year (4). The combination of carboplatin plus paclitaxel has also been investigated in phase II trials, with response rates of 56% to 63% (25, 26). However, all these combinations have not yet proven an improvement in survival or quality of life of patients. In fact, combination chemotherapy regimens in endometrial carcinoma should be approached with care with respect to toxicity. Many women with endometrial cancer are elderly (median age at diagnosis is 60 to 65 years), obese and diabetic. All these factors increase the risk of complications with more intensive chemotherapy. In addition, many of them have had adjuvant pelvic radiotherapy with the consequent limited hematological reserve, and therefore dose-intense regimens should be administered with caution.

Biologic and molecular-targeted therapies have no proven role at this time in the treatment of relapsed or metastatic endometrial carcinoma. The most tantalizing results have been obtained with mTOR inhibitors [temsirolimus (5, 27-29), everolimus (30) and deforolimus (31)], with a response rate in chemotherapy-naïve patients of up to 26% for temsirolimus. Results in pretreated patients are less encouraging, with a clinical benefit rate of 44%, but objective response rate equal or lower than 7% (29, 30).

In summary, despite the use of combinations or novel agents and therapies, responses in patients with advanced/metastatic endometrial cancer are of short duration. Thus, progression-free survival (PFS) of 6-9 months and overall survival (OS) of 12-15 months have been found with first-line chemotherapy (6). As expected, shorter PFS (2 months) and OS (6-8 months) have been found with second-line regimens (8, 13). Therefore, treatment of advanced/metastatic endometrial cancer is a clearly unmet medical need and investigation of new agents is warranted. Results found in phase I studies with PM00104 (Zalypsis[®]; see Section 1.3.5.4.2) suggest that this novel chemotherapeutic agent can be of value as chemotherapy in this disease setting.

